## 1. Background

Type 1 diabetes is an autoimmune disease characterized by chronic hyperglycemia resulting from an absolute endogenous insulin deficiency. In type 1 diabetes management, premeal insulin dosage and physiological insulin requirement must be matched to maintain optimal blood glucose control (1). Intensive insulin therapy is the preferred treatment for individuals with type 1 diabetes. It can be an effective way of controlling blood glucose levels and minimising the risk of long term diabetic complications (2, 3). Insulin delivery is achieved subcutaneously using multiple daily injections or subcutaneous insulin infusion using insulin pumps. It provides the calculation of insulin doses according to the carbohydrate content of the meal and pre-meal blood glucose levels. It can also provide a less restricted lifestyle to individuals with type 1 diabetes by providing flexibility in meal time, quantity and frequency (4, 5).

Achieving glycemic control is important for patients with diabetes because it effects the development of diabetic complications. Diabetes control is mainly assessed according to HbA1c, fasting blood glucose and blood glucose measured two hours after meal consumption. In the control of type 1 diabetes, not only regular use of insulin is sufficient, but also important in balanced diet and regular physical activity. An individualized diet plan in particular is the corner-stone to proper metabolic control (6).

Currently, there are algorithms based on the carbohydrate content of the meal to calculate the meal insulin dose in patients with type 1 diabetes receiving intensive insulin therapy. One of these algorithms, the carbohydrate counting method (CC), is considered the “gold standard” for estimation of meal-time insulin dose. CC assumes that only carbohydrates influence the dose of insulin required and that equal portions of carbohydrate produce a similar glycemic response and require the same amount of exogenous insulin to be metabolized (7, 8). However, the effects of carbohydrates in food on increasing blood glucose levels are not equal and this concept is defined as glycemic index (GI). Studies have shown that GI is also a parameter affecting blood glucose level (9). The GI value of the food together with the CC provides the most accurate estimation of the insulin response in determining the meal insulin dose (7, 8, 10). Despite the use of insulin therapy and CC in individual with type 1 diabetes, many individuals continue to experience unanticipated hyperglycaemic and hypoglycaemic events that increase the risk for development of complications and reduce quality of life. These complications occur especially after a high-protein or high-fat meal is consumed. Although carbohydrate is the predominant macronutrient affecting postprandial blood glucose level, recent research has shown that dietary fat and protein can significantly affect the postprandial glucose excursions and thus adjusting the prandial insulin dose for these macronutrients may be beneficial (10-13).

Food Insulin Index method (FII), which is another method used to determine meal insulin dose, has been proposed which ranks foods based on the insulin response in healthy subjects relative to an isoenergetic reference food (either glucose or white bread) (14). The algorithm uses food energy as the constant, and thus all dietary components and their metabolic interactions can be considered for any food with sufficient energy density, allowing a holistic approach to determining insulin demand. It has shown that FII is more advantageous than CC in the control of postprandial blood glucose levels in people with type 1 diabetes especially after high fat and

protein meal (1, 8, 12, 13, 15). In addition, it was found that there was a correlation between meal insulin dose calculated according to FII and observed insulin response (1).

In summary, it is important to maintain blood glucose levels within the normal range in individuals with type 1 diabetes. In order to achieve this, the insulin demands of the foods consumed in the meal must be estimated accurately. Today, CC method is used in the calculation of meal insulin dose. GI is also known to affect blood glucose levels. Knowing the GI of foods together with CC provides the most accurate estimate of insulin response. However, the CC is insufficient to calculate the insulin dose, especially for high-fat or high-protein meals. It has been shown that the newly developed FII method which determines insulin demand by using energy of nutrients is advantageous compared to carbohydrate counting method in keeping blood glucose levels within normal range. However, studies have not evaluated the effect of GI on blood glucose levels when comparing CC and FII method.

## **2. Objective**

The aim of this study is to compare the impact of carbohydrate counting (CC) method which is standard insulin dose calculation algorithm and food insulin index (FII) method which is a new algorithm on postprandial glucose following high fat and high protein meals with different GIs in adolescent with type 1 diabetes.

## **3. Materials and methods**

[figure not shown]
### *3.1. Study Design*

A home-based, randomized, single-blind and crossover trial included 14 adolescents aged 14-18 years with type 1 diabetes. All participants were sent to their homes for 4 consecutive days with a different glycemic index breakfast. The insulin doses of the meals were calculated according to CC and FII methods. Test breakfasts with different GIs and insulin requirements calculated with different algorithms are as follows: High GI calculated by CC (CHGI), low GI calculated by CC (CLGI), high GI calculated by FII (FHGI) and low GI calculated by FII (FLGI). The order of the test meals and insulin algorithms was determined by using a computer-generated randomization sequence before recruitment. The test diets prepared by the dietitian were given to the participants by the diet company before the test day. Test meals were served as a breakfast after 8-hours fasting and participants were asked to consume the meal in full, within 20 min. The breakfast plates were collected and weighed after the test day. On the day before each test meal, participants were instructed to eat an evening snack meal at 22:00 h and to refrain from eating and/or drinking (except for water) and/or doing any physical activity beyond that of their typical daily activities. Participants started to consume test meals at 07.00 h. They were asked not to consume any food other than breakfast for postprandial 240 min. Participants maintained their normal activity levels during the study days. The classification of meals according to insulin dose calculation methods is shown in the Figure 1.

This study was conducted according to the guidelines laid down in the Declaration of Helsinki. The Clinical Research Ethics Committee of the Erciyes University approved the protocol (2018/607) on 21 November 2018, and all participants gave written informed consent.

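### Evening-snack content and morning activity are not held the same across a participant's four test days, which adds avoidable within-person noise in a 14-person crossover

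*Combined protocol and SAP*

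**What the plan says.** Section 3.1 (Study Design) opens: "A home-based, randomized, single-blind and crossover trial included 14 adolescents aged 14-18 years with type 1 diabetes". Each participant has four conditions on four consecutive days, in a computer-generated random order.

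The same section already fixes a good deal:

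- the fast: "Test meals were served as a breakfast after 8-hours fasting"
- the start: "Participants started to consume test meals at 07.00 h"
- the meal itself, to be finished within 20 min, with plates collected and weighed
- other food: "They were asked not to consume any food other than breakfast for postprandial 240 min"

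Two things are looser. On the day before each test meal "participants were instructed to eat an evening snack meal at 22:00 h". What the snack contained, and how much of it was eaten, is not stated. Participants were also told to refrain from "doing any physical activity beyond that of their typical daily activities", and for the study days themselves the section says "Participants maintained their normal activity levels during the study days". It describes no activity record.

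Section 4 (Measurement of blood glucose) takes a capillary reading at t=0 and every 30 min to 240 min. Section 6 (Statistical Analysis) summarises the four hours as a trapezoidal AUC and compares conditions by a one-way repeated-measures analysis. It names no adjustment for t=0 glucose and does not say whether the AUC is total or incremental.

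**The concern.** A crossover gains its efficiency from comparing a person with themselves, so anything that differs between a participant's mornings, apart from meal and dose, goes into the error term. The snack is the last intake before the fasting reading, and a different snack can move starting glucose. Activity between 07:00 and 11:00 falls inside the window from which the AUC is computed. An instruction to stay within normal activity sets a level that may itself vary from day to day; it does not ask for four similar mornings.

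What is at stake is precision. With 14 participants and no stated sample-size calculation, there is no visible margin for noise that could be avoided at almost no cost. The planned analysis, as written, has nothing to absorb a shift in starting glucose.

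**Working it through.** **Which conditions are the same on all four mornings?**

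| Condition | Source | Held the same? |
|---|---|---|
| Fast | 3.1 | Yes: 22:00 to 07:00 is 9 h less snack time, consistent with the stated 8 h |
| Start of meal | 3.1 | Yes, 07:00 |
| Eating time, completeness | 3.1 | Yes, 20 min, plates weighed |
| Other food to 240 min | 3.1 | Yes, none |
| Snack time | 3.1 | Yes, 22:00 |
| Snack content and amount | 3.1 | Not stated |
| Activity 07:00-11:00 | 3.1 | Normal level; no record described |
| Starting glucose | 4, 6 | Measured at t=0, not named in the analysis |

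**Is the plan's own precision figure reproducible?** There is none to reproduce. The documents give N = 14 and a 0.05 threshold, but no SD, effect size or power. What follows is illustrative.

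**Interval width.** Let f be the share of within-person variance due to snack and activity, and suppose it is wholly removed. Relative width = √(1 − f).

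- f = 0.10: √0.90 = 0.949, about 5% narrower
- f = 0.30: √0.70 = 0.837, about 16% narrower

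**Power.** For a paired comparison with n = 14 and two-sided alpha 0.05 (two-sided is assumed; section 6 does not say), the noncentral t distribution gives 80% power at a standardised paired difference of 0.81. Adding a nuisance share f shrinks that difference to 0.81 × √(1 − f).

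| f | Standardised difference | Power, n = 14 | n for 80% power |
|---|---|---|---|
| 0 | 0.81 | 80% | 14 |
| 0.10 | 0.77 | 76% | 16 |
| 0.30 | 0.68 | 65% | 20 |

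A rough check on the last column: 14/0.90 = 15.6 and 14/0.70 = 20.

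**Noise or bias?** In 50,000 simulated four-condition crossovers with 14 participants and no true effect, adding independent day-to-day noise equal to the rest of the within-person variance raised the SD of the contrast between algorithms from 1.00 to 1.41 (√2). Mean bias stayed at about 0 and type I error at about 0.050 with and without the noise. This holds when snack and activity do not depend on the assigned condition.

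**The case against.** The strongest reply is that the trial is deliberately home-based and already well controlled, and that asking for normal activity is itself a consistency condition. Because the days are consecutive, the day before test meals 2, 3 and 4 is test day 1, 2 and 3, so the limit on extra activity may also cover three of the four measurement windows. Fingersticks every 30 min restrict the morning further. Much of this stands, and it is why the point is minor. But a ceiling on activity does not make mornings alike, and none of it bears on snack content.

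Four stronger readings are tempting and are not supported:

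- *The snack was free choice.* The text is silent on content; silence does not establish choice.
- *Mornings mixed school and home.* The documents mention neither school nor weekdays.
- *The comparison is biased.* With randomised order, noise of this kind falls on either algorithm by chance. Participants could see their readings, the two breakfasts are visibly different, and "The test diets prepared by the dietitian were given to the participants by the diet company before the test day", so behaviour could in principle respond to condition. Nothing in the documents shows that it did.
- *Lows after an active morning would be charged to one algorithm.* Section 4 does exclude readings after a hypoglycaemic event, but under randomisation such lows would strike either algorithm. That exclusion is a separate analysis question, whatever the activity rule.

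It is also fair to say that the 10-30% share has no support in the documents, and that no practical measure would remove all of it.

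**Conclusion.** The point holds as a low-cost improvement. Snack content and morning activity are not held the same across a participant's four test days, and section 6 names no adjustment for starting glucose. The expected consequence is lost precision with 14 participants, not bias, provided snack and activity do not depend on the assigned condition. Its size is unknown. The 5-16% narrowing rests on an assumed 10-30% variance share and complete removal, so it illustrates what each assumed share would mean and does not estimate the effect in this trial.

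**What to change.** In section 3.1:

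1. Have each participant repeat their own first-evening snack, same content and amount, at 22:00 before all four test days.
2. Ask each participant to keep their own usual 07:00-11:00 activity the same on all four mornings, and to note departures on the sheet where glucose values are recorded.
3. Where possible, choose four consecutive days with a similar morning routine.

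In section 6, include that day's t=0 glucose as a covariate in the repeated-measures analysis of AUC. It changes from day to day, so a mixed model with condition as a fixed effect and participant as a random effect is the natural form. With complete data this takes one of (14 − 1) × (4 − 1) = 39 within-person error degrees of freedom. It can absorb the part of the snack effect that acts through starting glucose, but not activity after t=0.

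The cost is a modest burden on participants and slightly less free-living conditions. No rest or activity rule after the insulin dose is proposed. The document is written in the past tense; if the data are already collected, the covariate can still be specified, and the report can state what is known of snack and activity and name the limitation.

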### 3.2. Participants

All participants underwent a detailed physical examination by the pediatric endocrinologist before included in the study. Fourteen adolescents with type 1 diabetes who attended the outpatient clinic of the Pediatric Endocrinology, at the Child Hospital of Erciyes University, Kayseri, Turkey were selected on the basis of the following criteria: aged between 14-18 years adolescents, type 1 diabetes diagnosed for at least one year (1, 8, 11, 14-16), performing self-monitoring of blood glucose and doses of insulin at least four times daily (17, 18), HbA1c  $\leq$  9.6% for the last three months (19), negative fasting C-peptide ( $<0.1$  nmol/L) (20), total daily insulin use of  $\geq 0.5$  U/kg (19), World Health Organization BMI/age z-score of -1 to below 3 (21). Exclusion criteria included complications of diabetes or other medical conditions including celiac disease (11, 13), treatment with oral hypoglycaemic agents (11), food allergies, intolerances, or eating disorder (1, 8, 17), intestinal malabsorption (22), delayed gastric emptying (20), viral or bacterial infection, physical or mental disability (22, 23), clinical condition related to impaired digestive system such as cystic fibrosis (19, 22).

**Figure 1.** The classification of meals according to insulin dose calculation methods

### 3.3. Test Meals

The energy content of the test meals was calculated according to the recommended energy requirement for adolescents between the ages of 14-18 in Turkey's Dietary Guidelines. In addition, according to the principles of adequate and balanced nutrition, breakfast meals should meet 1/4-1/5 of daily energy requirement (24, 25). Therefore, the energy of the test meals was determined about 560 kcal. The energy, carbohydrate, protein, fat and FII of the test meals were the same; GI were different. The participants were given 75 ml of whole milk, 22 g hot dog, 60 g cheddar cheese, 75 g white bread and 8 g seedless raisins for breakfast with high glycemic index; 30 g Ezine cheese, 65 g boiled eggs, 13 g peanut, 20 g whole grain bread, 55 g apple, 185 g strawberry yogurt and 100 ml skimmed milk for breakfast with low glycemic index. The energy and macronutrient composition of the test meals is given in the Table 1.

GI and FII of foods in test meals were estimated by using the GI and FII for 1000-kJ portions of foods tables published by Bao et al. (26), with glucose as the reference food. The average meal GI and FII were calculated as follows (27):

$$\text{Meal GI} = \frac{\sum_{a=1}^n \text{GI}_a \times \text{AvCHO}_a \times \text{Frequency}_a}{\sum_{a=1}^n \text{AvCHO}_a \times \text{Frequency}_a} \quad \text{Meal II} = \frac{\sum_{a=1}^n \text{II}_a \times \text{Energy}_a \times \text{Frequency}_a}{\sum_{a=1}^n \text{Energy}_a \times \text{Frequency}_a}$$

	Meal with high glycemic index	Meal with low glycemic index
Total energy (kcal)	555	561
Carbohydrate (g)	61.8	61.6
Carbohydrate (%)	45	45
Protein (g)	22.6	22.3
Protein (%)	17	17
Fat(g)	23.1	23.3
Fat (%)	38	38
Glycemic Index	64	35
Food Insulin Index	45	45

**Table 1.** The energy and macronutrient composition of the test meals

### 3.4. Calculation of insulin dose of test meals:

The insulin dose of the meals was calculated by 2 different methods.

#### 3.4.1. Carbohydrate Counting

Insulin carbohydrate ratio (ICR) was determined for each participant. The participant's individualized ICR, expressed as insulin units per 15 g carbohydrate portion, was used to calculate insulin dose (28, 29).

#### 3.4.2. Food Insulin Index

Insulin dose was calculated from the Food Insulin Demand (FID). The FID is the mathematical product of the FII and the energy content (kJ) per serving divided by 1000 (FID = FII x kJ per serving/ 1000). The FID was scaled up by a factor of 100/59 (FID of 1000 kJ of pure glucose/grams of carbohydrate in 1000 kJ of pure glucose) so that insulin could be dosed in the same ratio as each participants' individualized ICR (1, 11)

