### *6. Statistical Analysis*

Statistical analysis was performed using the Statistical Package for the Social Sciences (version 22.0; IBM SPSS Statistics) software. Data were expressed as the number (n) and percentage (%) for categorical variables, and means  $\pm$  SDs, medians (25th-75th percentiles) for continuous variables. Normality was assessed using the Shapiro- Wilk test. Furthermore, continuous variables were examined for skewness and kurtosis, and log-transformed before analysis and reported back-transformed geometric means (G)  $\pm$  standard error (S.E) when required (33). Differences between groups were tested using t-tests. The blood glucose profile during the 4-h postprandial period was quantified as area under the curve (AUC) calculated according to the trapezoidal rule. A one-way repeated measure was used to analyse between the comparable test conditions. For all statistical analyses, p values less than 0.05 were considered to have statistical significance (8).

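### Section 3.4.2 inverts the food insulin index conversion: dosing with a ratio per 15 g carbohydrate needs FID × 59/100, not × 100/59

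*Combined protocol and SAP*

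**What the plan says.** Section 3.4.2 defines food insulin demand as "FID = FII x kJ per serving/ 1000". It then says "The FID was scaled up by a factor of 100/59" and explains that factor as "FID of 1000 kJ of pure glucose/grams of carbohydrate in 1000 kJ of pure glucose". The purpose given is "so that insulin could be dosed in the same ratio as each" participant's own ICR. Section 3.4.1 gives the unit of that ratio: "expressed as insulin units per 15 g carbohydrate portion".

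Section 3.1 says only that "The insulin doses of the meals were calculated according to CC and FII methods". Section 3.3 says of the two breakfasts that "The energy, carbohydrate, protein, fat and FII of the test meals were the same; GI were different", and Table 1 lists their contents. The documents give no FID for either meal, no ICR values, no worked dose and no insulin units administered. Section 6 tests for differences only ("p values less than 0.05 were considered to have statistical significance") and sets no equivalence margin.

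**The concern.** The factor is a number of FID units divided by a number of grams. Multiplying an FID by FID units per gram does not produce grams, yet grams are what an ICR per 15 g needs. The direction of the conversion therefore looks reversed.

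This sentence is the only dosing rule in the documents for two of the four conditions (FHGI and FLGI), in a home-based trial in adolescents. If it was followed literally, the FII doses were far too large and the comparison would show a unit error rather than the merit of the food insulin index. Section 4 also drops glucose data after a hypoglycaemic event, so overdosing could remove data selectively from the FII conditions.

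If the right conversion was used, the published rule is still wrong for anyone who applies it. A second issue then appears: whether the two algorithms gave different doses for these meals at all.

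**Working it through.** **Inputs**
- Section 3.4.2: FID = FII × kJ / 1000, and the factor 100/59.
- Section 3.4.1: ICR in units per 15 g carbohydrate.
- Table 1: energy 555 kcal (high GI) and 561 kcal (low GI), carbohydrate 61.8 and 61.6 g, protein 22.6 and 22.3 g, fat 23.1 and 23.3 g, FII 45 for both.
- Assumptions: 4.184 kJ per kcal, and energy taken either as printed or rebuilt at 4/4/9 kcal per gram.

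**The stated factor on its own reference food.** 100/59 = 1.695 FID units per gram. The 59 is reasonable: at an assumed 17 kJ/g, 1000/17 = 58.8 g. For 1000 kJ of glucose, FID = 100 × 1000/1000 = 100, and a valid conversion must return 59 g.
- As written: 100 × 100/59 = 169.5.
- Inverted: 100 × 59/100 = 59.

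The written and correct rules differ by (100/59)² = 2.87. Scaling the 15 g portion instead of the FID gives 15 × 100/59 = 25.4 FID units per portion, which is the same as FID × 59/100.

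**The test meals.** Rebuilt energy:
- High GI: 4(61.8) + 4(22.6) + 9(23.1) = 545.5 kcal.
- Low GI: 4(61.6) + 4(22.3) + 9(23.3) = 545.3 kcal.

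FID = 45 × kcal × 4.184 / 1000.

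| | High GI, printed | Low GI, printed | High GI, 4/4/9 | Low GI, 4/4/9 |
|---|---|---|---|---|
| Energy (kcal) | 555 | 561 | 545.5 | 545.3 |
| FID | 104.5 | 105.6 | 102.7 | 102.7 |
| FID × 100/59 | 177.1 | 179.0 | 174.1 | 174.0 |
| FID × 59/100 (g) | 61.7 | 62.3 | 60.6 | 60.6 |
| Carbohydrate counted (g) | 61.8 | 61.6 | 61.8 | 61.6 |
| As written / counted | 2.87 | 2.91 | 2.82 | 2.83 |
| Corrected / counted | 1.00 | 1.01 | 0.98 | 0.98 |

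**Rounding.** Let FII run from 44.5 to 45.5, energy vary by ±0.5 kcal and macronutrients by ±0.05 g, over both energy bases. The as-written ratio then runs from 2.78 to 2.94. The corrected value runs from 59.8 to 63.1 g, at most about 3% from the counted carbohydrate in either direction.

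**In insulin units.** At an assumed ICR of 1 U per 15 g:
- As written: 174.0/15 = 11.6 U to 179.0/15 = 11.9 U.
- Carbohydrate counting: 61.8/15 = 4.1 U.
- Corrected: the largest gap from carbohydrate counting is about 3.2% of 4.12 = 0.13 U. That is 0.07 U at an assumed 0.5 U per 15 g and 0.4 U at 3 U per 15 g.

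**A third possibility.** FID dosed at the ICR with no conversion gives 104.5/61.8 = 1.69 and 105.6/61.6 = 1.71 times the carbohydrate-counting dose on printed energy.

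**The case against.** The best reply is that this is a misdescription and not a misdosing. The sentence states its purpose and names pure glucose as the anchor, so a trained reader can recover the intended step: the 15 g portion, not the FID, is scaled up by 100/59. The conversion is also referenced to two sources that cannot be consulted here. On this view the threefold dose measures an ambiguity and is not a likely event. The point about dose contrast is a separate design matter. It applies only if dosing was right, it rests on rounded table values, and the plan announces no equivalence claim. Finally, the text is in the past tense, so a table of doses is a request about reporting.

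Much of this stands. Nothing in the documents shows that an excessive dose was given, and a wording error is possible. The sign of the small corrected difference is undetermined. But the sentence scales the FID, not the portion, and its own reference food contradicts it. No other section corrects it, and without a dose or ICR the benign reading cannot be confirmed. The dose-contrast point is secondary and conditional, but it survives rounding and either energy basis.

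**Conclusion.** The concern holds. The rule is wrong as written, on the plan's own definitions and without any outside source. Taken literally, it makes the FII dose 2.8 to 2.9 times the CC dose for both meals. With the correct factor the two doses agree to within about 3%. Both figures rest on Table 1 and 4.184 kJ per kcal, and both hold on printed or rebuilt energy. The statements in insulin units also depend on assumed ICRs.

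Which conversion was used cannot be determined from the documents. Either answer matters. Literal use would mean overdosing and an invalid comparison. Correct use would mean almost no dose contrast between the algorithms for these meals, so a non-significant result from the planned difference tests could not be read as equivalence.

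**What to change.** Replace the conversion sentence in Section 3.4.2 with: *FID was multiplied by 59/100 to give carbohydrate-equivalents in grams (equivalently, the 15 g ICR portion was scaled up by 100/59 to about 25.4 FID units).* Add the check that 1000 kJ of glucose returns 59 g.

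Then go to the dose records and establish whether FID was multiplied by 100/59, multiplied by 59/100 or left unconverted. Report the conversion used and the insulin units given in each of the four conditions.

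If the correct factor was used, add one limitation: the FII and CC doses for these meals agree to within about 3%, so a non-significant difference does not show that the methods are equivalent.

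The cost is one corrected sentence, one arithmetic check, a review of existing records, a short table and possibly one limitation sentence. It needs no extra participants, visits or procedures and no change of meals.
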